UX007 dosing will be targeted at 35% of total daily caloric intake throughout the study. Subjects receiving a different dose of UX007 at study entry may continue treatment at the current established dose. If a subject has been off UX007 treatment for > 1 month, the dose may be titrated at the discretion of the investigator. Enrolled subjects are able to maintain standard of care treatment with up to 3 AEDs throughout the duration of the study.

OBJECTIVES:

The primary objective of the study is to:

- Evaluate the long-term safety of UX007 in Glut1 DS subjects

The secondary objectives of the study are to:

- Evaluate the long-term effect of UX007 efficacy on seizures associated with Glut1 DS
- Evaluate the long-term effect of UX007 on health-related quality of life related to Glut1 DS

ENDPOINTS:

The primary endpoint of the study is:

- Frequency of adverse events (AE) and serious adverse events (SAE) assessed as related to study drug over the Treatment Extension Period

General secondary endpoints of the study are:

- Frequency of seizures over the Treatment Extension Period
- Measures of neurological function over the Treatment Extension Period
- Health-related quality of life over the Treatment Extension Period

NUMBER OF SUBJECTS PLANNED:

The study will enroll approximately 40 pediatric, adolescent, and adult subjects who have completed the UX007G-CL201 study and, at the discretion of the Sponsor, additional subjects who participated in other clinical studies, ISTs, or expanded access/compassionate use treatment programs.

DIAGNOSIS AND CRITERIA FOR INCLUSION AND EXCLUSION:

Individuals eligible to participate in this study must meet all of the following criteria:

- 1) Diagnosis of Glut1 DS as indicated by cerebrospinal fluid glucose concentration, erythrocyte 3-O-methyl-D-glucose uptake assay, or molecular genetic testing obtained from medical records.
- 2) Males and females, aged at least 1 year at the time of informed consent
- 3) Completion of UX007G-CL201 study (NCT01993186). Glut1 DS patients who received UX007/triheptanoin treatment as part of other clinical studies, ISTs, or expanded access/compassionate use treatment programs may be eligible at the discretion of the sponsor.
- 4) Provide written informed consent or verbal assent (if possible) with written informed consent by a legally authorized representative after the nature of the study has been explained, and prior to any research-related procedures

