3.5 Sample Size Considerations

This study will enroll up to 40 pediatric, adolescent, and adult Glut1 DS subjects who have completed the UX007G-CL201 study and, at the discretion of the Sponsor, additional subjects from participated in other clinical studies, ISTs, or expanded access/compassionate use treatment programs. The sample size is intended to provide the maximum amount of information regarding UX007 long-term safety, along with indicators of sustained efficacy and durability of response in Glut1 DS patients.

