8 STATISTICAL METHODS OF ANALYSES

8.1 General Principles

All statistical tests will be two-sided and tested at statistical significant level of 0.05. The statistical analyses will be reported using summary tables, figures, and data listings. Continuous variables will be summarized by number of subjects and mean, standard deviation (SD), median, minimum, and maximum values. Categorical variables will be summarized by number and percentage of subjects. All raw data obtained from the CRFs will be included in data listings. In general, analysis will be performed for Rollover subjects and Non-Rollover subjects, separately.

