8.8 Efficacy Analysis

Because the primary objective of this study is to evaluate the long-term safety, the efficacy parameters will not be grouped into primary or secondary categories. Efficacy analyses will be based on the Full Analysis Set.

- Seizure frequency

For Rollover subjects, frequency of seizures (normalized to a 4-week rate) up to first year will be analyzed using generalized estimating equations (GEE), with reduction from baseline for each visit period (see Section 7.2.5, Table 4) as the response variable, baseline as covariates, visit period (in UX007G-CL202 study) as a factor, identity link function and exchangeable within subject working correlation matrix.

Frequency of seizures will be derived for each subject based on subject seizure type. Observable seizures from the diary will be used for Observable Seizures Subjects. For Absence Seizures Only Subject, the absence EEG data measured at the scheduled visit (matching the each period end time specified for seizure diary, see Section 7.2.5, Table 4) will be used, e.g., scheduled Month 3 EEG absence seizure data will be used to assess seizure frequency for visit period Month 0 – 3.

For Non-Rollover subjects, descriptive statistics of observed value will be presented.

- Seizure frequency from diary

For Rollover subjects, observed value and reduction from baseline in frequency of observable seizure and absence seizure (normalized to a 4-week rate) for each visit time period (see Section 7.2.5, Table 4) will be summarized by subject group and subject seizure types.

For Non-Rollover subjects, descriptive statistics of observed value will be presented.

- Seizure frequency from EEG

For Rollover subjects, observed value and reduction from baseline in frequency of absence seizure and non-absence seizure (normalized to a 24-hour rate) for each visit time point (see Section 7.2.5, Table 4) will be summarized by subject group and subject seizure types.

For Non-Rollover subjects, descriptive statistics of observed value will be presented.

For Rollover subjects, descriptive statistics for observed value and change from baseline will be presented by assessment time point for the following endpoints:

- CNS total score
- SF-10 summary scores
- SF-12 domain/summary score

For Non-Rollover subjects, descriptive statistics of observed value will be presented.

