10 APPENDICES

10.1 Appendix A. Efficacy Endpoint Summary Table

Endpoint	Statistical Method	Analysis Population
Reduction from baseline in frequency of seizures up to first year	GEE	FAS (Rollover subjects)
Frequency of seizures	Descriptive statistics	FAS (Rollover subjects)
Frequency of seizures	Descriptive statistics	FAS (Non-Rollover subjects)
Frequency of observable/absence seizures by seizure diary	Descriptive statistics	FAS
Frequency of absence/non-absence seizures by EEG	Descriptive statistics	FAS
CNS total score	Descriptive statistics	FAS
SF-10 summary scores	Descriptive statistics	FAS – SF10
SF-12 domain/summary score	Descriptive statistics	FAS – SF12v2

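### The only seizure model in SAP 8.8 is a GEE on at most about 40 subjects with no small-sample method named, so its intervals and p-values can be anti-conservative if it is run in the usual way

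*SAP*

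**What the plan says.** For Rollover subjects, SAP 8.8 says that seizure frequency "up to first year will be analyzed using generalized estimating equations (GEE), with reduction from baseline for each visit period" as the response. Baseline is a covariate and visit period a factor, with "identity link function and exchangeable within subject working correlation matrix". Appendix A lists "Reduction from baseline in frequency of seizures up to first year" as the only efficacy row analysed by GEE; every other row is descriptive.

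On size, SAP 3.5 states "This study will enroll up to 40 pediatric, adolescent, and adult Glut1 DS subjects who have completed the UX007G-CL201 study", and the protocol synopsis gives a similar figure: "The study will enroll approximately 40 pediatric, adolescent, and adult subjects who have completed the UX007G-CL201 study". Both then allow further subjects from other sources at the sponsor's discretion. Neither document gives the number of Rollover subjects. SAP 8.1 adds "In general, analysis will be performed for Rollover subjects and Non-Rollover subjects, separately", so Non-Rollover subjects do not enter the GEE.

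On the level, SAP 8.1 says "All statistical tests will be two-sided and tested at statistical significant level of 0.05". SAP 7.4 names SAS but no procedure or option. Protocol 7.6.4 leaves the choice of tests to the SAP.

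**The concern.** A working correlation matrix points to the robust (sandwich) variance. With few clusters that variance is biased downward, and a normal or chi-square reference ignores the sampling error of the variance estimate. Both effects make intervals too narrow and p-values too small.

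This is the only model that addresses seizures. The protocol synopsis says the secondary analyses are meant to evaluate whether the effect is maintained. An analyst who followed SAP 8.8 in the default way could report a reduction, or a change between Year 1 periods, with more confidence than the data support.

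**Working it through.** The documents contain no sample-size or error-rate calculation to reproduce. The 0.05 is a chosen level, so the check is whether the planned model attains it.

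**Inputs from the documents.** There are four Year 1 visit periods (SAP Table 4), so the period factor has 3 df. The mean parameters are intercept, baseline and three period terms, which makes 5. There are at most about 40 clusters (SAP 3.5), and the level is 0.05 two-sided (SAP 8.1).

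**Assumed.** Cluster counts n of 20-40, the data shape, and an uncorrected sandwich Wald test.

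**Step 1: one period contrast, normal and complete data.** Baseline is constant within a subject, so it cancels. The contrast is the mean within-subject difference, and its sandwich variance uses divisor n. The true level is 2·P(t(n−1) > 1.960·√((n−1)/n)).

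**Step 2: joint 3-df period test, same data.** The test rejects when W > 7.815. Under the null, (n−3)·W/(3n) follows F(3, n−3), which gives the cut-offs below.

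| n | t cut-off | Contrast level | F cut-off | Joint level |
|---|---|---|---|---|
| 40 | 1.935 | 6.0% | 2.410 | 8.2% |
| 30 | 1.927 | 6.4% | 2.344 | 9.5% |
| 20 | 1.910 | 7.1% | 2.214 | 12.4% |

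At a one-sided 0.05, which is what Protocol 7.6 states, the contrast level is 5.6% at 40 and 6.3% at 20.

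**Step 3: simulation of the full GEE.** This used 2,500 runs per cell and an assumed 7% dropout per period. The corrected version is a Mancl-DeRouen variance with a t or F reference on n−5 df.

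| Data, n | Contrast, uncorrected | Contrast, corrected | Joint, uncorrected | Joint, corrected |
|---|---|---|---|---|
| Normal, 40 | 6.7% | 5.3% | 8.9% | 5.9% |
| Normal, 30 | 6.0% | 4.0% | 10.0% | 5.8% |
| Normal, 20 | 7.4% | 4.2% | 13.8% | 5.6% |
| Log-normal, 40 | 4.8% | 3.5% | 6.0% | 3.0% |
| Log-normal, 30 | 5.0% | 2.9% | 6.9% | 3.3% |
| Log-normal, 20 | 4.1% | 1.6% | 8.0% | 2.2% |

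Gamma-Poisson rates give the same picture. Across the skewed cases the joint test ran at about 4-11%. The uncorrected contrast was 6.0% or less, falling to 3-4% as skewness rose.

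**Step 4: mean reduction from baseline per period.** Under assumed skewed rates with no true reduction, the uncorrected test rejected in 12-20% of runs, against 8.5-10% with Mancl-DeRouen and t. The correction therefore helps but does not restore 5%. Part of the remainder is not a small-sample effect. The standard error of the mean reduction at the average baseline treats that average as known, although baseline is also part of the response. How much excess remains depends on the assumed overdispersion.

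**Step 5: test type.** A generalized score statistic equals W/(1+W/n). In the setting of steps 1 and 2, its level is 4.9% (contrast) and 4.3% (joint) at n=40, and 4.7% and 3.4% at n=20.

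**The case against.** The strongest objection is that the SAP plans neither of the period tests in steps 1 and 2. It makes visit period a factor but names no period contrast and no joint hypothesis. The largest normal-data figures therefore belong to a test that a reader would have to supply. This stands, and it is why the fix asks for the estimates to be named.

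Normal data are also the less relevant case. Protocol 7.5.2.1.1 describes some patients with daily seizures and others with gaps of up to months, so rates will be strongly skewed between subjects. With such rates a single contrast shows little or no excess. This stands for the contrast. It does not stand for the mean reduction, where skewness makes matters worse.

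A reader might infer that the stated 0.05 is simply not delivered, or that a Year 1 change would be declared too often. The documents do not support that without conditions. They fix neither the Rollover count nor the test type, and a score test would be slightly conservative for the period tests. Nor do they establish that the GEE has fewer than 40 clusters, because the 40 can be read as Rollover subjects alone.

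Finally, the consequence is limited. Protocol 7.5.2 treats all efficacy endpoints as secondary, SAP 8.8 does not rank them, Protocol 7.6.9 disclaims power for comparisons, and Protocol 7.6 makes no multiplicity adjustment. No decision rule hangs on these p-values. This stands and lowers the weight of the point.

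**Conclusion.** The concern holds conditionally. If the GEE is run with an uncorrected robust Wald test and a normal or chi-square reference, its intervals and p-values can be anti-conservative at this size. For normal data and 20-40 subjects, the level is about 6-7% for one period contrast and 8-12% for a joint period test. For skewed rates, the contrast is near or below 5%, the joint test about 4-11%, and the per-period mean reduction 12-20%. All of this assumes the Rollover count, the data shape and the Wald test. The weight is minor to moderate: the model is the plan's only seizure inference, but efficacy is not primary and the study is not powered for comparisons.

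**What to change.** In SAP 8.8, state that GEE standard errors use a small-sample-corrected sandwich variance, such as Mancl-DeRouen or Kauermann-Carroll. Intervals and single estimates should use a t reference, and any joint period test an F reference, with denominator df equal to Rollover subjects minus mean parameters (n−5 here). Name the estimates to be reported: the mean reduction for each period, and any period contrast. While editing, reconcile the two-sided level in SAP 8.1 with the one-sided level in Protocol 7.6.

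The change is a sentence or two and a software setting. The statistical costs are these:

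- **Wider intervals.** The t quantile alone adds about 4% at 40 subjects (2.030/1.960 = 1.036) and 9% at 20 (2.131/1.960 = 1.087). For a period contrast with complete data, Mancl-DeRouen multiplies the standard error by a further n/(n−1). The totals are 1.036 × 40/39 = 1.06 and 1.087 × 20/19 = 1.14.
- **Less power to detect waning when rates are very skewed.** In a simulation with a 60% rise in seizure rate by the last period and between-subject log-SD 1.5, the correction cut contrast power from 31% to 19% at 20 subjects and from 41% to 33% at 30. Joint-test power fell from 30% to 11% and from 37% to 24%.
- **Incomplete repair.** The correction reduces the excess for the mean reduction but does not remove it, so those p-values should still be read with caution.

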4.2 Efficacy Endpoints

- Reduction from baseline in frequency of seizures (normalized to a 4-week rate) during the study: Observable seizures from the diary will be used for Observable Seizures Subjects. For Absence Seizures Only Subject (See Section 5.7), the absence EEG data measured at the scheduled visit will be used.
- Observed value and reduction from baseline in frequency of observable seizure and absence seizure (normalized to a 4-week rate) by seizure diary
- Observed value and reduction from baseline in frequency of absence seizure and non-absence seizure (normalized to a 24-hour rate) by EEG
- Observed value and change from baseline in CNS total score
- Observed value and change from baseline in SF-10 summary scores
- Observed value and change from baseline in SF-12 domain/summary score
- Plasma levels of UX007 metabolites

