5.7 Classification of Subjects at Baseline by Seizure Type for Rollover Subjects

For UX007G-CL201 rollover subjects, the classification of subjects defined at randomization during UX007G-CL201 study will be used.

- **Observable Seizures Subject:** a subject who meets any of the following:
 - Observable seizure frequency (types A, B, C, D, E, F, G, H, I, J, K and L; see Section 5.6: Table 2) greater than or equal to 4 during the baseline period.
 - Observable seizure frequency less than 4 at randomization and absence seizure frequency less than 4 during the baseline period
- **Absence Seizures Subject:** a subject who meets any of the following:
 - has seizure types M, N, O or P (see Section 5.6: Table 2) recorded on the seizure diary during the baseline period
 - has absence seizures documented on the screening EEG
 - Absence seizure frequency (see Section 5.6, Table 2 and Section 5.8.2) greater than 0 during the baseline period

All subjects will either be an Observable Seizures Subject, an Absence Seizures Subject, or both. Since there is potential overlap, the following definitions are used to classify enrolled subjects into three mutually exclusive groups:

- **Observable Seizures Only Subject:** a subject who is an Observable Seizures Subject *but not an Absence Seizure Subject*
- **Absence Seizures Only Subject:** a subject who is an Absence Seizures Subject *but not an Observable Seizure Subject*
- **Both Seizures Subject:** a subject who is both an Observable Seizures Subject and an Absence Seizure Subject

Classification by seizure type at baseline is not defined for Non-Rollover subjects since all subjects in UX007G-202 study had prior treatment exposure to UX007 and there is no seizure diary measurement data prior to the initial UX007 treatment for Non-Rollover subjects.

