5.8 Derived Seizure Efficacy Variables

5.8.1 Observable/Absence Seizure Frequency by Diary

Observable/Absence seizure frequency from the diary (normalized to a 4-week rate), is defined as:

$$\text{Observable/Absence Seizure Frequency} = \frac{\text{Total number of seizures}}{\text{Number of days observed}} \times 28$$

See Section 5.6, Table 2 for the list of observable/absence seizure types from diary that are counted. For analyses, observable/absence seizure frequency from the diary will be defined for every 3 month during Year 1 and every 6 month during Year 2 and 3. Refer to Section 7.2.5, Table 3 for visit window mapping for seizure frequency by diary.

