5.8.2 Absence/Non-absence Seizure Frequency by EEG

The absence/non-absence seizure frequency from EEG (normalized to a 24-hour rate) is defined as:

$$\text{Absence/non-absence Seizure Frequency} = \frac{\text{Total number of seizures}}{\text{Number of hours observed}} \times 24$$

See Section 5.6, Table 2 for the list of absence/non-absence seizure types that are counted. Refer to Section 7.2.5, Table 3 for visit window mapping for seizure frequency by EEG.

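### SAP 8.8 pools diary seizure rates and single-EEG absence rates in one GEE with no source term, and defines neither the reduction nor the step from the 24-hour EEG rate to the 4-week rate

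*SAP*

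**What the plan says.** SAP 8.8 plans one GEE for Rollover subjects over the first year, "with reduction from baseline for each visit period" as the response and "baseline as covariates, visit period (in UX007G-CL202 study) as a factor, identity link function and exchangeable within subject working correlation matrix". Observable Seizures Subjects enter with diary counts for the whole visit period. For the rest: "For Absence Seizures Only Subject, the absence EEG data measured at the scheduled visit (matching the each period end time specified for seizure diary". The Month 3 EEG, for example, stands for Months 0–3. No term for data source or seizure type is listed, and SAP 4.3 names no covariates.

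SAP 4.2 labels the combined endpoint "Reduction from baseline in frequency of seizures (normalized to a 4-week rate) during the study". The two component rates are on different time scales:

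- SAP 5.8.1, diary: "Observable/Absence seizure frequency from the diary (normalized to a 4-week rate), is defined as" count over days observed, times 28.
- SAP 5.8.2, EEG: "The absence/non-absence seizure frequency from EEG (normalized to a 24-hour rate) is defined as" count over hours observed, times 24.

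No section converts the second into the first, and none gives a formula for reduction. Protocol 7.6.4 leaves the specific analyses to the SAP. SAP 7.2 sets no minimum EEG length and uses whatever recording time is complete. In Appendix A this GEE is the only efficacy analysis that is not descriptive.

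**The concern.** Two programmers could follow this text and report different results, because both the response and the unit of one of its two sources are open. On the most natural reading (absolute difference, EEG rate multiplied by 28) the model averages quantities of very different size and precision. The baseline covariate adjusts for level, but it does not separate the sources or allow for unequal variance. At stake is what the one modelled efficacy result means: whether it describes the Rollover subjects as a whole or mainly the absence-only subjects among them.

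**Working it through.** **1. The plan's own figure.** SAP 7.2.5 gives a 3-month period as (365.25/12) × 3 ≈ 92 days. The product is 91.31, so 92 is a rounding up. The scheduled days 92, 184, 276 and 368 are exact multiples of 92.

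**2. What one event is worth.** The diary formula gives 1/92 × 28 = 0.30 per 4 weeks. The EEG formula gives 24/H per 24 hours for a recording of H hours. The documents do not give H, so a range is assumed, with an unwritten factor of 28.

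| H (assumed) | per 24 h | per 4 weeks, ×28 | ratio to one diary seizure |
|---|---|---|---|
| 24 h | 1 | 28 | 92 |
| 12 h | 2 | 56 | 184 |
| 8 h | 3 | 84 | 276 |

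**3. Precision.** With Poisson counts at the same true rate r per 4 weeks, the variance is r × 28/92 for the diary and r × 28 × 24/H for one EEG. The ratio is again 92 × 24/H. At r = 28 the SDs are 2.9 (diary) and 39.6 (12 h EEG).

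**4. Effect of the missing definitions.** Assumed: 24 diary and 8 EEG subjects, true reductions of 30% and 50%, median baselines of 20 per 4 weeks (diary) and 20 per 24 hours (EEG), 12 h EEG, 300 simulated GEE fits. The mean pooled estimate is 100.7 with absolute reduction and ×28, and 9.5 with absolute reduction and the 24-hour rate kept. With percent reduction it is 30.6% or 30.4%, because the factor cancels.

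**5. Baseline level.** One route into the Observable group in SAP 5.7 is an observable frequency of at least 4. The other is "Observable seizure frequency less than 4 at randomization and absence seizure frequency less than 4 during the baseline period". A subject outside both therefore has observable frequency below 4 and absence frequency of at least 4. If that 4 is an EEG rate per 24 hours, the baseline is at least 4 × 28 = 112 per 4 weeks. The unit is an inference. The pointer to SAP 5.8.2 stands in a different bullet, "Absence seizure frequency (see Section 5.6, Table 2 and Section 5.8.2) greater than 0 during the baseline period", and SAP 5.8.1 also defines an absence frequency, by diary per 4 weeks.

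**6. Consequence for the planned model (illustration).** Assumed:

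- absolute reduction, ×28, 12 h EEG, 42-day diary baseline and four 92-day periods;
- medians of 15 per 4 weeks (diary) and 10 per 24 hours (EEG);
- lognormal subject rates (SD log 1.2 and 1.0), period-to-period SD log 0.2–0.6, Poisson counts;
- observed baseline of at least 4 in each source's own unit.

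The contrast is the Year 1 mean reduction against zero. With balanced data and a centred baseline, the robust statistic is z = mean reduction ÷ (√Σe²/n), where e is a subject's residual from the regression of mean reduction on baseline. Tests are two-sided at 5%; ranges cover 26+4 and 24+8 diary + EEG subjects.

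| Truth | pooled model | same model, diary subjects alone |
|---|---|---|
| diary halves, EEG unchanged | about 27–46% | about 95–100% |
| both halve | about 87–100% | about 95–100% |
| no change | about 20–31% | about 16–24% |

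**7. Why the no-change row exceeds 5%.** In diary subjects alone, a small-sample robust SE with a t reference lowers rejection from 17–23% to 8–12%. Keeping the covariate and adding the variance from the estimated mean baseline (slope variance) gives 2–4%. A t test without the covariate gives 3.1–5.7%. The excess is thus partly small-sample robust-SE error and partly the treatment of the mean baseline as known. None of the detection rates in step 6 is power at a true 5% level.

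**The case against.** - **EEG is the right tool for absence seizures.** The protocol synopsis makes it the primary method. This stands; the issue is pooling it with diary rates.
- **The 4-week label implies ×28, and reduction beside observed value implies a difference.** Both are reasonable readings, but neither is written. If percent was intended, scale dominance disappears and only the mixing of sources is left.
- **Separate summaries exist.** SAP 8.8 tabulates reduction from baseline for diary and for EEG, by seizure type. This stands. A reader might infer that the pooled model hides a real change in diary subjects. It does not: that change would still be visible, though only descriptively.
- **The model works when both groups respond.** A reader might infer a general loss of power from pooling. The planned covariate model does not show that; the loss appears when the absence-only subjects do not respond.
- **The floor of 112 looks documentary.** It depends on a unit that SAP 5.7 does not state, for a classification carried over from the feeder study. The per-event figures do not depend on it.
- **The size rests on assumptions.** This stands. The number of Absence Seizures Only Subjects, the seizure rates, the EEG hours and the feeder-study baseline length are not in the documents, and the number of such subjects may be zero.

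**Conclusion.** The textual defect is certain: one model, two sources, no source term, no written conversion and no definition of reduction. The consequence is conditional. With absolute reduction and ×28, one EEG event weighs 92 to 276 times one diary seizure, and a handful of absence-only subjects can dominate the pooled estimate. In the illustration, detection falls from about 95–100% to about 27–46% when only diary subjects improve, which is not far above the pooled model's own 20–31% rejection with no change. Little is lost when both groups improve. SAP 8.8 also does not name the tested contrast; if it is mean reduction against zero, the robust z test rejects too often even without pooling. Because safety is primary, SAP 8.8 leaves efficacy unranked and protocol 7.6.9 claims no power, this should be fixed but does not threaten the study's main purpose.

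**What to change.** Amend SAP 4.2, 5.8.2, 8.8 and Appendix A:

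(a) Define reduction as absolute or percent. If percent, add a rule for a zero baseline, since SAP 5.7 admits Observable Seizures Subjects who are below 4 on both measures.

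(b) Fit the model separately for Observable Seizures Subjects (diary, per 28 days) and Absence Seizures Only Subjects (EEG, per 24 hours, without ×28). Keep visit period as a factor so that maintenance over time is still shown.

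(c) Name the tested contrast. If it is mean reduction against zero, use a small-sample t-based test that accounts for the estimated mean baseline. Dropping the baseline covariate is one way; keeping it and adding the slope variance is another.

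The cost is SAP wording and model code, with no new data. The price is the loss of a single pooled estimate and an imprecise absence-only result, which should be reported as an estimate with a confidence interval and a caution about the small number of subjects.
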